For reporting purposes, regulatory event documentation will be aggregated into central reports using REDCap's "Reports" functionality. The "Reports" functionality allows data to be pulled from the Regulatory Event forms and summarized in one central report. The content of these reports and the frequency in which they are distributed to regulatory bodies is outlined in sections F3b. and F3c.

F3b. AE Reporting

Research staff will generate reports summarizing all AEs for each participant using the REDCap "Report" feature outlined above in section F3a. The report will contain the participant's code number, date of AE, severity, attribution level to study, action taken, and outcome. These

adverse events will be provided quarterly in this format to the DSMC, UW IRB, and NCCIH in accordance with requirements.

F3c. SAE/Unanticipated Problem Reporting

- Unanticipated fatal or life-threatening SAEs at least possibly related to study procedures will be reported immediately to the NCCIH Program Officer, Chair of the DSMC, and the UW IRB.
- Breaches of confidentiality or inappropriate access to protected health information will be reported to the NCCIH Program Officer, Chair of the DSMC, and the UW IRB within 24 hours.
- Other unanticipated SAEs or serious problems at least possibly related to study procedures will be reported to the NCCIH Program Officer and DSMC Chair within 5 days, and to the UW IRB within 10 days.
- Anticipated or unrelated SAEs will be reported to the DSMC and NCCIH Program Officer as part of the annual DSM report.

Research staff will record all SAEs and unanticipated problems using the Regulatory Event form outlined above in section F3a. These serious adverse events/problems will be summarized using the REDCap “Report” format and provided quarterly in this format to the DSMC, the UW IRB, and NCCIH in accordance with requirements.

The Chair of the DSMC will be contacted when an SAE/unanticipated problem is discovered to receive consultation on the matter. The Chair of the DSMC will use her discretion to determine whether the other DSMC members should also provide additional consultation.

F4. Data Quality and Safety Review Plan and Monitoring

F4a. Description of Plan for Data Quality and Management

Data collected by research staff will be entered directly into a database created in REDCap, a secure HIPAA-compliant web-based system. Web forms will be created to enhance functionality and proper data entry. The REDCap system also allows researchers to create an audit trail, as well as capture an e-signature from research staff attesting to the validity of the data entered (in instances where an e-signature is specified).

All group treatment sessions will be audio recorded to ensure compliance to treatment procedures. These recordings may also be used for training purposes. A portion of treatment sessions will be randomly selected to be reviewed by study researchers to ascertain fidelity to protocol. Study clinicians will receive feedback as needed if they diverge from protocol.

In addition, research study staff will review the study data in detail on a quarterly basis to detect any systematic issues with data collection and protocol compliance. Data types that will be reviewed include participant accrual, status of enrolled participants, adherence data regarding study assessments and intervention, any protocol deviation or violation that warrants a note-to-file, and AEs, SAEs, and unanticipated problems.

Regarding protocol deviations, only participant study visits completed outside of the protocol-defined windows would be considered protocol deviations; non-completion of study components by participants would not result in protocol deviations. This was approved by the NCCIH PO on 5/25/2018.

F4b. Frequency of Data Review

The frequency of data review for this study differs according to the type of data and can be summarized in the following table:

Data type	Frequency of review	Reviewer
Participant accrual	Quarterly	Co-PIs, Chair of DSMC
Status of all enrolled participants	Quarterly	Co-PIs, Chair of DSMC
Participant adherence to study procedures	Quarterly	Co-PIs, Chair of DSMC
AEs	Quarterly	Co-PIs, Chair of DSMC
SAEs	Per occurrence	Co-PIs, Chair of DSMC, NCCIH, UW IRB
Unanticipated Serious Problems	Per occurrence	Co-PIs, Chair of DSMC, NCCIH, UW IRB

F4c. Participant Accrual and Compliance

Review of the rate of participant accrual and compliance with inclusion/exclusion criteria will occur monthly during the first six months of recruitment and then every three months to ensure that a sufficient number of participants are being enrolled to allow for an adequate test of the primary study hypotheses and that they meet eligibility criteria.

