Chronic pain is a common and costly condition affecting millions of Americans, and spine pain (including back and neck pain) is the most common chronic pain condition. Although various psychosocial treatments are effective for chronic pain, there is a critical lack of research examining if these treatments work via the mechanisms specified by theory. Three of the most common components of pain treatments are: (1) Cognitive Therapy (CT); (2) Mindfulness Meditation (MM), and (3) Activation Skills (AS). Theoretically, CT targets unhelpful cognitions (cognitive content, i.e., pain catastrophizing), MM targets how patients think (cognitive process, i.e., non-judgmental awareness), and AS targets what people do (i.e., more “well” behaviors”). However, we do not know if these techniques are effective via these specific mechanisms, or via shared mechanisms. Knowledge concerning treatment mechanisms is critical for modifying treatments to focus on the mechanisms that have the greatest benefits for the most patients. Further, understanding the mechanisms underlying post-treatment maintenance of gains and relapse will advance capacity to optimize long-term beneficial outcomes.

Actigraphy and ecological momentary assessment (EMA) consisting of multiple daily measures allows for the evaluation of longitudinal mechanism effects. In the context of a clinical trial, use of actigraphy and EMA data could determine the specific lag times of mechanism effects (i.e., how long it takes for a change in a mechanism to influence key outcomes). Thus, utilizing actigraphy and EMA throughout a controlled trial represents an innovative approach to assessing psychosocial pain treatment mechanisms at a micro-level.

A2. Specific Aims and Hypotheses

In the planned trial, 300 individuals with chronic pain including low back pain as a primary or secondary pain problem will be randomly assigned to telehealth-delivered CT, MM, or AS. Mechanisms and outcomes will be assessed with actigraphy and twice daily EMA during baseline, treatment, and for 4-weeks post-treatment. Mechanisms of longer-term maintenance of gains will be evaluated at 3- and 6-month follow-up. Given past research showing equivalent efficacy for active treatments, we expect no significant group level outcome differences between conditions. However, we do expect *individual* variability in treatment response and maintenance of gains that will allow us to examine mechanisms of change. This study will address two aims.

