The 2-Week Baseline Monitoring Period will consist of an approximately 14-day period before the participant begins his/her first session of treatment. We will schedule all participants to start the Baseline Monitoring Period 14 days before the start of the first group of that cohort. This means, for example, if the first session of CT will be 4/16, the first session of MM will be 4/17, and the first session of AS will be 4/18, all participants will begin the Baseline Monitoring Period on 4/2, which is 14 days before the start of the first group (4/16). Participants will complete Baseline EMA surveys until the day before their first treatment session.

The 2-Week Baseline EMA survey asks questions on pain interference, pain catastrophizing, cognitive processes, average pain intensity during the past 12 hours, mood, pain self-efficacy, sleep/wake times, and activity level and activity monitor wear. On days before Session 1 in the evening EMA there will also be questions on treatment credibility and expectancies. Each EMA survey should take approximately 5 minutes to complete. There are a minimum of 28 EMA surveys for the participant to complete during the Baseline EMA Monitoring Period.

The Treatment Monitoring Period begins on the day the participant is scheduled for Session 1 and ends the day s/he is scheduled for Session 8. The Treatment EMA survey asks the same questions as the 2-Week Baseline EMA survey described above, with the addition of items on therapeutic alliance, group cohesion, and time spent practicing skills learned in treatment. The therapeutic alliance and group cohesion items will be added after the Session 4 and 8 evening EMAs, while the time spent practicing skills items will be asked daily during the evening EMA beginning with Session 1. Additionally, items on treatment credibility and expectancies will be asked once again after Session 1 and before Session 2. While not collected as data, there is also an additional question asked the evening before each treatment session on whether the participant has completed his/her homework activities; this question is used as a reminder to prompt participants to complete their homework activities if they have not already done so.

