Participants who are not randomized will be asked to mail back any ActiGraphs still in their possession. Randomization will use a covariate-adaptive randomization scheme. We will use a procedure proposed by Pocock and Simon (see Chapter 9 of Randomization in clinical trials: Theory and practice, 2nd edition, 2016, by W.F. Rosenbeger and J.M. Lachin, John Wiley and Sons), with the objective of balancing the covariate in the marginal distributions. The covariates for the covariate-adaptive randomization will be sex, baseline pain interference score (mild/moderate or severe), and low back pain (LBP) type (primary or secondary pain).

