The implementation of the procedure will be accomplished by using a statistical program, such as R. The study statistician will write the program and will be responsible for running the randomization for each cohort; the statistician may also train another staff member to be a backup randomizer should s/he be unavailable to randomize participants for a cohort (e.g., away on vacation and cannot access the program). When a new cohort is ready to be randomized, the staff responsible for enrollment of the participants will provide the statistician with a list of participants (identified by dummy ID number and not their actual subject ID number) with their respective values of the covariates (sex, pain interference at baseline, and LBP pain type). The statistician will randomize according to the Pocock and Simon procedure, and return the list to the staff member responsible for creating the treatment groups according to the assignments. The staff member will then match the dummy ID numbers with the list containing the actual subject ID numbers. For example, the staff member responsible for enrollment may send a list of dummy IDs A, B, and C to the statistician. There will be a separate list (which the statistician does not have access to) linking subject ID to the dummy ID (e.g., A = 800009, B = 812349, C = 822229). The statistician will randomize A, B, and C to treatment and send back these assignments to the staff member; the staff member will then input the subject ID into the randomization list by matching the dummy ID to the subject ID. There is no potential for staff bias to interfere with creating these lists or randomizing participants. ***This is because the staff member conducting randomization will never have access to any person level information (other than sex, pain interference category, and LBP type), nor will the staff member have any direct communication with study participants at any point.*** Further, even if the staff member was familiar with person level details, this would not impact the structure of the randomization list, given that the order in which participants from each block are randomized is determined automatically by the program created by the statistician. To further safeguard against potential bias, individuals will be randomized in the order that they become eligible for randomization (based on the completion of the pre-randomization procedures). After a participant has been randomized, the research staff member in charge of data entry will update the randomization form in REDCap to reflect the participant's treatment allocation. Only staff members who do not have access to study data during participant enrollment will know

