
which treatment intervention corresponds with which group. Research staff will complete an electronic randomization case report form for each randomized participant that will be included with study data. The master list of participants will also be updated with the participant's assignment.

An unblinded staff member will call the participant to convey assignment and the schedule of treatment sessions. Brief (1 page) reading material specific to the treatment group will also be made available to the participant in preparation for Session 1; the reading material is informative only and not home practice. The group schedule and reading material will be provided to the participant electronically, unless the participant requests otherwise. The unblinded staff member may also provide the participant part or all of their participant treatment handbook prior to the first session (excluding instances in which the treatment mandates that a given portion of the treatment materials not be provided before a particular treatment session).

Research staff will re-screen participants on approved mutable eligibility criteria (e.g., pain intensity, frequency, etc.) if three months or more has elapsed between the consent process and randomization.

D6l. Treatment Scheduling

Cohorts of study treatment groups will be offered 3-5 times per year.

Trained clinicians will commit to offering at least three groups per year: one of each treatment type. This will reduce the potential for therapist bias on the outcomes.

An unblinded staff member will maintain lists of group assignments and coordinate the scheduling of sessions. Staff will provide clinicians with a list of participants who were assigned to each class. Treatment reminders will be provided for each session using the participant's preferred method of communication. If a participant misses a session, the therapist or another staff member may contact the participant about the missed session. If the therapist or other staff member is not able to get a hold of the participant, additional follow-up may be conducted by research staff.

D6m. Treatment

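### The mechanism SEMs have no prespecified cohort term, so calendar trends shared by a cohort can inflate the b path if they move the early mechanism and late interference slopes together

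*Combined protocol and SAP*

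**What the plan says.** **Basis of inference.** A2 anticipates no outcome difference between arms and relies on individual "variability in treatment response and maintenance of gains that will allow us to examine mechanisms of change".

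**Calendar.** D6l: "Cohorts of study treatment groups will be offered 3-5 times per year". D2 puts enrolment at about 3.5 years. D6j: "We will schedule all participants to start the Baseline Monitoring Period 14 days before the start of the first group of that cohort". In its example CT starts on 4/16, "the first session of MM will be 4/17, and the first session of AS will be 4/18", and the Treatment Monitoring Period "begins on the day the participant is scheduled for Session 1". Under D6k the statistician "will be responsible for running the randomization for each cohort", so each cohort is divided among all three arms.

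**Model.** D6s reduces each variable to a within-person slope per 14-day epoch (early treatment days 15–28, late treatment days 29–42; days 43–56 and 57–70 for Aim 2). The model has two treatment dummies (paths a1 and a2) and a path b from the early mechanism slope to the late interference slope. If both a paths are non-significant they are removed, and a significant b is then taken to support the Shared Mechanisms Model.

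**Covariates.** D6s says only that relevant covariates will be tested and adjusted for where warranted. Table 3 lists one covariate, whether low back pain is the primary or a secondary problem. D6s also plans an exploratory look at emotional responses to COVID-19. Cohort, season and calendar time are not named. Figure 3 is not shown, so this reading rests on the text.

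**The concern.** Path b is an observational association between people; randomizing treatment does not protect it. Members of a cohort live through almost the same weeks. A seasonal change in activity, a holiday period or a change in pandemic restrictions can tilt the slopes of a whole cohort at once, and D2's timeline (2017 to 2022) spans the pandemic. Because each cohort spans all arms, the treatment dummies cannot absorb such a shift.

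If cohorts whose early mechanism slopes are shifted also tend to have shifted late interference slopes, that between-cohort covariance is pooled into b and read as individual-level change. The likely misreading is specific: a trend common to all arms gives a significant b with no treatment difference in the mechanism, which is the pattern D6s assigns to a shared mechanism.

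**Working it through.** **1. Number and size of cohorts.** 3 × 3.5 = 10.5 and 5 × 3.5 = 17.5, so about 10 to 17 cohorts. At N = 240 that is 240/17.5 ≈ 14 to 240/10.5 ≈ 23 people each.

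**2. The plan's own figures (Table 5).** For the mediation rows take joint significance, r = .30 for each path, two-sided alpha (assumed), and the smallest n with [Φ(atanh(.30)·√(n−3) − z)]² ≥ .80. This gives 111, 131 and 142 at alpha .050, .025 and .0167. A noncentral t gives 107, 126 and 137–138. The plan states 109, 129 and 140. The interaction rows (f² = .15, two tested predictors, noncentral F) give 93, 98 and 102, exactly as stated. Table 5 is not at fault.

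**3. Size of a spurious b.** Let cohort explain a share s of the variance of both slopes, and let ρ be the correlation between the cohort shift in the early mechanism slope and that in the late interference slope. With no person-level link, the expected correlation is about ρ × s. For s = .10 and ρ = .9 that is about .09, against the planned .30. Neither s nor ρ is in the documents; both are assumptions. For scale, s = .10 means a between-cohort SD of √(.10/.90) = .33 of the within-cohort SD; s = .05 gives .23 and s = .02 gives .14.

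**4. False-positive rate of b.** Simulation: late slope regressed on early slope plus two arm dummies, true b = 0, N = 240, cohorts crossed with arms, 4,000 runs per setting. Rejection at .05 without a cohort term, 10 / 17 cohorts:

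| s | ρ = 0 | ρ = .5 | ρ = 1 |
|---|---|---|---|
| 2% | 4.9% / 5.2% | 6.0% / 4.6% | 6.6% / 5.8% |
| 5% | 5.6% / 5.5% | 7.0% / 7.1% | 12.8% / 11.7% |
| 10% | 7.6% / 6.2% | 13.2% / 13.0% | 31.3% / 32.6% |

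Runs with 12 cohorts of 20 and ρ capped at .9 give about 5–6% at s = 2%, 6–11% at 5%, and 6–7%, 13% and 26–27% at 10% for ρ = 0, .5 and .9. With cohort fixed effects the rate is 4.4–5.4% in every setting of the 10- and 17-cohort runs.

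**5. Would testing for cohort first be enough?** With m = 240/K people per cohort, the F-test of cohort at .05 has power P(F > Fcrit / [1 + m·s/(1−s)]). At s = 5% this is 57% (10 cohorts) to 49% (17 cohorts); at s = 10%, 86% to 83%. A screen would often miss a cohort effect that matters.

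**6. Cost of the adjustment.** Replace n−3 in step 2 by n−3−k, with k = (K−1) + 2 for the cohort terms and arm dummies. Required n becomes 122, 142 and 153 (K = 10) or 129, 149 and 160 (K = 17), all below 240. Power for b at r = .30 and N = 240 is 99.6% at .05 and 98.6–98.8% at .0167. At r = .20 it goes from 88% to about 86% at .05 (noncentral t, 238 against 223–227 df).

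**The case against.** **The bias is conditional.** A reader might infer that leaving cohort out biases b as a matter of fact. The documents do not support that. The variables are slopes, so a constant seasonal level drops out, and b links two variables in two different fortnights. An event confined to one epoch need not correlate the two shifts. With ρ = 0, b is unbiased and only its standard error is affected. This stands. On the other side, the epochs are adjacent: a trend lasting four weeks tilts both slopes, and a dip and rebound tilts them in opposite directions, so correlated shifts are plausible without being shown.

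**The size is assumed, and the simulated test is simpler than the SEM.** Both stand. If the hidden model also conditions on the early interference slope, part of a shared shift may be absorbed. The plan also adjusts alpha over six tests. At .0167, s = 10% and ρ = .5 give 6.2–6.5%: a lower absolute rate than 13%, but almost four times nominal.

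**The covariate clause leaves room for cohort.** True. The fair criticism is that cohort is not prespecified, and step 5 shows why a test-then-adjust rule is a weak substitute. The COVID-19 exploration concerns individual emotional responses and does not stand in for calendar time.

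**Other stronger readings.** The minimisation rule omits cohort: "The covariates for the covariate-adaptive randomization will be sex, baseline pain interference score (mild/moderate or severe), and low back pain (LBP) type". A reader might blame it, but balancing cohort across arms would protect the a paths and do nothing for b. Nor are members of a cohort measured on exactly the same days: after the common baseline start, each group follows its own sessions. The changes of entry rules in the revision history alter who enters; nothing there shows that they shift both slopes together.

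**Conclusion.** The gap is real but modest. As described, the Aim 1 and Aim 2 SEMs pool between-cohort and within-cohort association into b, and nothing in the plan commits to separating them. Whether b is actually distorted depends on two quantities that the documents do not give. The inflation is negligible if cohort explains about 2% of slope variance. At 5% the false-positive rate at .05 is about 6–11%, and at 10% about 6–26%, for correlations from 0 to .9. The upper ends need strongly correlated shifts. The planned sample size is not in question. This is a minor improvement, worth making because it removes a rival explanation of a primary result at almost no cost.

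**What to change.** In D6s:

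- Prespecify cohort as a fixed effect, or centre each slope on its cohort mean with degrees of freedom reduced to match, in every equation of the Aim 1 and Aim 2 SEMs.
- Treat it as a design factor that stays in the model whatever a significance screen shows.
- State that b is a within-cohort coefficient.
- Report the model without cohort as a sensitivity analysis.

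The cost is a change of SAP wording and 9–16 degrees of freedom. Participants are already organised by cohort, so no new data and no larger sample are needed.
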